8.7.2. Secondary Objectives

8.7.2.1. Explore the Differences in Demographic and Clinical Characteristics Between TOFA Index Prescription OOP Costs and TNFi Cycling with ETN and ADA vs. TOFA Switching Cohorts

For this objective descriptive analysis will be conducted. The goal of this objective will be to describe the respective cohorts and explore the presence of demographic and clinical characteristics differences between the cohorts that will inform multivariable analyses. Known demographic characteristics (eg, age, gender, geographic location) will be summarized. In addition, other patient characteristics (eg, pre-index RA medication use and medical history, comoribidity status, cumulative/index OOP costs) will be evaluated. Index medication prescriber, regimen, and OOP costs will also be described.

8.7.2.2. Compare Treatment Patterns Including Dosing, Adherence, Persistence Treatment Patterns Between TOFA Index Prescription OOP Costs and TNFi Cycling with ETN and ADA vs. TOFA Switching Cohorts

For this objective, treatment patterns will be summarized across the cohorts of interest. Specific treatment patterns include changes in use of concomitant NB-DMARDs, number and proportion of patients in the five treatment persistent groups (persistent, switch immediately, discontinue and switch, discontinue and restart, discontinue and no switch or restart), switch anytime, or effectively treated (meeting each of 6 Curtis algorithm criteria) as well as times to immediate and anytime switch and discontinuation. Times to discontinuation, switching or either will be assessed with Kaplan-Meier curves and Cox proportional hazards models. 8723 Compare All-Cause and RA-Related Health Care Utilization Between TOFA

8.7.2.3. Compare All-Cause and RA-Related Health Care Utilization Between TOFA Index Prescription OOP Costs and TNFi Cycling with ETN and ADA vs. TOFA Switching Cohorts

For this objective descriptive analysis will be conducted. All-cause and RA-related pharmacy and medical resource utilization measures (flags and 12-month counts) will be presented per patient during the 12-month baseline and follow-up periods. In addition, changes from baseline to follow-up will be evaluated.

8.7.2.4. Compare All-Cause and RA-Related Healthcare Costs Between TOFA Index Prescription OOP Costs and TNFi Cycling with ETN and ADA vs. TOFA Switching Cohorts

For this objective descriptive and multivariable analysis will be conducted. For the descriptive analysis, 12-month pre- and post-index cost measures will be presented per patient during the baseline and follow-up. The change in 12-month costs from the baseline to the follow-up will also be calculated. In addition, total all-cause cost will be presented in each of the months of the baseline and follow-up. The mean cost in each month will be included on a figure demonstrating the trend in costs over time. Multivariable analysis of follow-up health care cost will also be conducted using generalized linear models (see Section 8.7.4).

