8.7.3. Descriptive Analysis

All study variables, including pre- and post-index measures and changes in these measures, will initially be analyzed descriptively. In general, numbers and percents will be provided for dichotomous and polytomous variables, while means, medians, and standard deviations will be provided for continuous variables. Missing or unavailable data will not be imputed.

Results will be stratified by treatment cohort, bivariate comparisons of pre- and post-index measures will be provided, and appropriate tests (eg, t-test, Mann Whitney-U test, chi-square test) will be used based on the distribution of the measure. The analysis that is performed (ie, the methods that are used and the patients who are included) will be specific to the objective being examined. Descriptive techniques will be implemented for each objective.

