8.7.4. Multivariate Analysis

To control for possible confounding of the relationship between the outcomes and independent variable of interest, select objectives will be conducted utilizing multivariable methods as described above.

Final outcomes for multivariate analysis will be selected after review of descriptive results. Possible outcomes of interest include: total all-cause health care cost, total RA-related health care cost, cost of bDMARDs/tofacitinib/administration/NB-DMARDS, medication effectiveness (yes vs. no).

For each model, specific predictors to be included will be determined based upon clinical rationale and statistical significance. Variables listed in Section 8.3 will be considered for inclusion in the multivariable models. Additional variables identified throughout the course of the study will also be considered. Following standard procedure, regression diagnostics will be performed for each model to assess goodness of fit and violations of model assumptions (eg, multicollinearity, heteroskedasticity). When there are violations of the model, programmers will note them and make appropriate corrections to the data (ie, typically through transformation of either the independent or dependent variables) or in the method of estimation.

In particular, generalized linear models will be fit, using appropriate distributions and links for the nature of the data (eg, normally-distributed data with identity link, binary data and logit link). Results will be displayed on the original scale (that is, the inverse link). If sufficient sample size, tofacitinib IR and tofacitinib XR will be treated as separate groups. That is, contrast statements will be used to average the two groups when comparing to bDMARDs. Point estimates (that is, mean differences, ratios, odds ratios), 95 percent confidence intervals, and p- values will be presented for contrasts; ANOVA table will be presented to display the strength of the independent variables, including point estimates and p-values.

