8.7.6. Dichotomous Data

The probability of being effectively treated, persistent, and anytime switching to advanced therapy at one year will be modeled using logistic regression. Logistic regression models fit a maximum-likelihood logit model. For ease of interpretation, the results of logistic regression will be presented as odds ratios, 95 percent confidence intervals, and p-values for each covariate included in the final model.

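### Resource use is a comparative secondary objective in non-randomised cohorts, yet no adjusted model is named for it

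*Combined protocol and SAP*

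**What the plan says.** Section 7.2 sets out to compare the cohorts on post-index values and on post-minus-pre change. Its third bullet runs utilization and costs together, but Section 8.7.2.3 treats utilization as a comparison in its own right.

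The method for utilization is: "For this objective descriptive analysis will be conducted. All-cause and RA-related pharmacy and medical resource utilization measures (flags and 12-month counts) will be presented". These summaries cover both the year before and the year after index. Change is then added: "In addition, changes from baseline to follow-up will be evaluated". Section 8.7.3 then provides for bivariate comparisons in which "appropriate tests (eg, t-test, Mann Whitney-U test, chi-square test) will be used based on the distribution of the measure". The tests it names are two-group tests without covariates.

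The next objective, costs, is handled differently: "For this objective descriptive and multivariable analysis will be conducted". There too, "The change in 12-month costs from the baseline to the follow-up will also be calculated", but a generalized linear model (GLM) for follow-up cost is added.

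The modelling sections do not mention utilization:
- Section 8.7.4: "Possible outcomes of interest include: total all-cause health care cost, total RA-related health care cost", followed by a drug-cost measure and medication effectiveness.
- Section 8.7.5 covers costs.
- Section 8.7.6: "The probability of being effectively treated, persistent, and anytime switching to advanced therapy at one year will be modeled using logistic regression".

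The 8.7.4 list is not closed: "Final outcomes for multivariate analysis will be selected after review of descriptive results".

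**The concern.** This is a retrospective cohort study, and the plan itself gives control of confounding as its reason for multivariable methods (8.7.4). Section 8.1 also raises channeling of tofacitinib to later lines of therapy. Section 8.9 presents multivariable analysis as the control for observable differences between groups, but none is specified for utilization.

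If only the specified methods are run, the between-cohort p-values for outpatient visits, emergency visits and admissions will be unadjusted. A difference could then come from age, severity, comorbidity, insurance type or treatment history as easily as from out-of-pocket cost or from TNFi cycling. The specified comparisons use the pre-index value only as something tabulated or subtracted, never as a covariate.

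A related gap affects costs. Section 8.7.4 makes the Section 8.3 variables candidates for the models, to be chosen on clinical rationale and statistical significance. Pre-index cost may therefore be considered, but the plan does not commit to it.

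**Working it through.** **What is specified for each outcome family**

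| Outcome | Unadjusted summaries and tests | Named adjusted model |
|---|---|---|
| Costs | 8.7.2.4, 8.7.3 | Yes: 8.7.2.4, 8.7.4, 8.7.5 |
| Effectiveness | 8.7.2.2, 8.7.3 | Yes: 8.7.4, 8.7.6 |
| Persistence, any-time switch | 8.7.2.2, 8.7.3 | Yes: 8.7.6 |
| Resource use | 8.7.2.3, 8.7.3 | None |

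The data needed are already planned. Section 8.3.1 derives every utilization measure for the 12 months before index, and Section 8.3 derives the demographic, severity, comorbidity and prior-treatment variables.

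**Precision**

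The documents give no standard deviation, pre-post correlation or sample size (8.5 makes no formal computation), so there is no stated figure to reproduce. Assume equal pre and post variance (set to 1), cohorts of equal size and correlation r:
- unadjusted follow-up value: variance 1
- raw change: 2(1 − r)
- baseline value as covariate: 1 − r²
- covariate relative to change: (1 − r²) / [2(1 − r)] = (1 + r)/2

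| r (assumed) | Change | Covariate | Covariate / change | n per cohort: post / change / covariate |
|---|---|---|---|---|
| 0.3 | 1.40 | 0.91 | 0.65 | 393 / 550 / 358 |
| 0.5 | 1.00 | 0.75 | 0.75 | 393 / 393 / 295 |
| 0.7 | 0.60 | 0.51 | 0.85 | 393 / 236 / 201 |

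The last column is illustrative: a 0.2 SD difference, 80% power, two-sided 5%. Below r = 0.5 the raw change is noisier than ignoring baseline; above it, less noisy.

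With a standardized baseline imbalance d, covariate relative to change becomes about (1 + r)/2 × (1 + d²/4). At d = 0.5 this gives 0.69, 0.80 and 0.90 for r = 0.3, 0.5 and 0.7. The covariate loses its advantage only when d exceeds about 1.47, 1.15 and 0.84 respectively.

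A simulation of skewed counts (gamma-Poisson, mean 10, 300 per cohort, 3,000 runs, no effect, no imbalance, r about 0.48) gave SDs of the estimate of 1.18 (post only), 1.20 (change) and 1.02 (covariate, linear model).

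**Bias**

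- If cohorts differ at follow-up only through their baseline value, the post-only comparison is biased by r × d and the change by −(1 − r) × d. At r = 0.5 and d = 0.2 these are +0.10 and −0.10 SD.
- If instead the cohort difference is stable over time, the change is nearly unbiased and adjustment for baseline alone is not. The same simulation with a stable 20% difference and no effect gave mean estimates of +2.02 (post only), +0.05 (change) and +1.07 (covariate).

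**Which counts can take a baseline covariate**

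Inclusion criterion 1 excludes prior use of the index drug, and criterion 8 allows the cycling and switching cohorts one prior TNFi and no other advanced therapy. In ADA to ETN versus ADA to TOFA, pre-index ETN and TOFA fills are therefore zero for everyone, and the covariate would be constant. The same holds for ADA and TOFA fills in ETN to ADA versus ETN to TOFA.

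**The case against.** The strongest reply is that the choice is deliberate. Utilization is labelled descriptive, costs price the same services and receive a multivariable GLM, and Section 8.9 warns of unobservable differences. The 8.7.4 list is open, and pre-index use and cost are candidate covariates through Section 8.3.

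Part of this stands. A reader might infer that the plan rules out adjustment for utilization; it does not. But a utilization model added after the descriptive results have been reviewed would be a data-driven choice. A section headed as a comparison and supplied with two-group tests will also yield between-cohort p-values.

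A reader might also infer that subtracting baseline is simply wrong, or that it over-corrects. The working does not support that. Which method is less biased depends on an assumption the data cannot test, and under a stable cohort difference the change score did better. Nor does baseline use alone remove confounding, so it cannot be the only covariate. Change is, besides, a stated objective in Section 7.2 and should not be dropped.

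Finally, the variance ratios are linear-model results. They do not describe a log-link count model, which estimates a rate ratio, and they should not be read as the precision loss in this study.

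**Conclusion.** The point holds as a gap in specification. Resource use is compared between non-randomised cohorts with descriptive summaries, raw changes and unadjusted tests, and it is the only one of the outcome families tabulated above without a named adjusted model.

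The amount of confounding cannot be computed from the documents. The precision gain from a baseline covariate is indicative only: 0.65 to 0.85 of the variance of the change, and 0.91 to 0.51 of that of the unadjusted follow-up value, for assumed correlations of 0.3 to 0.7, equal variances and little baseline imbalance. The case for an adjusted model rests mainly on confounding, with precision as a secondary benefit.

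A reader might infer that the study's main conclusion is at risk. It is not: these outcomes are secondary, and the primary persistence analysis does not depend on them.

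**What to change.** In Sections 8.7.2.3 and 8.7.4:

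1. Prespecify a negative binomial model for all-cause and RA-related outpatient, emergency and inpatient counts, and logistic regression for the corresponding flags. Include cohort, the matching 12-month pre-index value and named Section 8.3 confounders, for example age, sex, insurance type, CIRAS, comorbidity score and, where there was a prior bDMARD, time since the first and last claim. The time-since terms do not apply to the advanced-therapy-naïve cohort.
2. Exclude index-drug fill counts from these models, because their pre-index value is zero by design.
3. Make pre-index cost a required covariate in the follow-up cost GLMs.
4. Keep post-minus-pre change as a descriptive or sensitivity result, and state that it and baseline adjustment rest on different untestable assumptions.

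If no model is wanted, the minimum is a sentence saying that the utilization results support no between-cohort inference.

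The cost is a few sentences plus further models and tables on variables already planned. Three visit types, two definitions (all-cause and RA-related) and at least three cohort comparisons give 3 × 2 × 3 = 18 count models or more, with the flags in addition.

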8.7.3. Descriptive Analysis

All study variables, including pre- and post-index measures and changes in these measures, will initially be analyzed descriptively. In general, numbers and percents will be provided for dichotomous and polytomous variables, while means, medians, and standard deviations will be provided for continuous variables. Missing or unavailable data will not be imputed.

Results will be stratified by treatment cohort, bivariate comparisons of pre- and post-index measures will be provided, and appropriate tests (eg, t-test, Mann Whitney-U test, chi-square test) will be used based on the distribution of the measure. The analysis that is performed (ie, the methods that are used and the patients who are included) will be specific to the objective being examined. Descriptive techniques will be implemented for each objective.

8.7.4. Multivariate Analysis

To control for possible confounding of the relationship between the outcomes and independent variable of interest, select objectives will be conducted utilizing multivariable methods as described above.

Final outcomes for multivariate analysis will be selected after review of descriptive results. Possible outcomes of interest include: total all-cause health care cost, total RA-related health care cost, cost of bDMARDs/tofacitinib/administration/NB-DMARDS, medication effectiveness (yes vs. no).

For each model, specific predictors to be included will be determined based upon clinical rationale and statistical significance. Variables listed in Section 8.3 will be considered for inclusion in the multivariable models. Additional variables identified throughout the course of the study will also be considered. Following standard procedure, regression diagnostics will be performed for each model to assess goodness of fit and violations of model assumptions (eg, multicollinearity, heteroskedasticity). When there are violations of the model, programmers will note them and make appropriate corrections to the data (ie, typically through transformation of either the independent or dependent variables) or in the method of estimation.

In particular, generalized linear models will be fit, using appropriate distributions and links for the nature of the data (eg, normally-distributed data with identity link, binary data and logit link). Results will be displayed on the original scale (that is, the inverse link). If sufficient sample size, tofacitinib IR and tofacitinib XR will be treated as separate groups. That is, contrast statements will be used to average the two groups when comparing to bDMARDs. Point estimates (that is, mean differences, ratios, odds ratios), 95 percent confidence intervals, and p- values will be presented for contrasts; ANOVA table will be presented to display the strength of the independent variables, including point estimates and p-values.

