8.7. Data Analysis

8.7.1. Primary Objectives

8.7.1.1. To Compare 12-month Post-Index Medication Persistence Duration (days) by TOFA Index Prescription OOP Costs and TNFi Cycling with ETN and ADA vs. TOFA Switching

For this objective both descriptive and multivariable analysis will be conducted. For the descriptive analysis, treatment persistence duration (days) with index medication at 12-months will be compared for those with low (\leq median) vs. high (> median) OOP costs and for those who switch from ADA to ETN vs. ADA to TOFA and ETN to ADA vs. ETN to TOFA.

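### Section 8.7.4 lets cohort results decide which outcomes are adjusted, names no primary adjusted model for persistence duration, and selects covariates partly by significance from a pool that includes post-index items

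*Combined protocol and SAP*

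**What the plan says.** **Outcomes.** Section 8.7.4 states: "Final outcomes for multivariate analysis will be selected after review of descriptive results". It continues: "Possible outcomes of interest include: total all-cause health care cost, total RA-related health care cost", and then adds drug and administration cost and the yes/no effectiveness measure. Section 8.7.3 describes the results to be reviewed: they are stratified by cohort, "bivariate comparisons of pre- and post-index measures will be provided", and tests are attached.

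**Commitments elsewhere.** For persistence duration, Section 8.7.1.1 says: "For this objective both descriptive and multivariable analysis will be conducted". It then specifies only the descriptive part. Section 8.7.2.4 says: "Multivariable analysis of follow-up health care cost will also be conducted using generalized linear models". Section 8.7.6 commits to logistic regression for effective treatment, being persistent, and any-time switching at one year.

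**Covariates.** Section 8.7.4 says "specific predictors to be included will be determined based upon clinical rationale and statistical significance", model by model, and "Variables listed in Section 8.3 will be considered for inclusion in the multivariable models". Variables identified later in the study may also be considered.

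**Two items labelled baseline in Section 8.3.** Index-medication OOP cost is taken for the first fill and also accumulated over follow-up months 1 to 12. Combination or monotherapy status depends on conventional DMARD use in the 90 days from the index date.

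**The concern.** The primary objective asks about the impact of OOP cost and of TNFi cycling in non-randomised cohorts, so the answer rests on adjusted estimates. Three features of the plan weaken them.

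- If the unadjusted cohort differences have been seen before it is decided which outcomes to adjust, the adjusted set can favour differences already observed.
- If a confounder's p-value helps decide whether it stays, a real confounder can be dropped because the cohort is small.
- If a covariate is measured after index and moves with the outcome, it is likely to pass a significance rule. Entering it can then remove part of a real persistence difference or create a false one.

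In addition, several models could serve for persistence and none is designated, so the scale of the main adjusted result could be settled after the data are seen.

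**Working it through.** The plan gives no sample size (Section 8.5), effect size or alpha, so there is no figure to reproduce. Steps 1 to 3 compare the text. Steps 4 and 5 are illustrations on assumed inputs.

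**1. Outcomes promised against outcomes left open**

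| Outcome | Firm commitment | Named in the Section 8.7.4 list |
|---|---|---|
| Persistence duration (primary) | 8.7.1.1 | no |
| Follow-up cost | 8.7.2.4 | yes, as possible |
| Effectiveness yes/no | 8.7.6 | yes, as possible |
| Persistent yes/no | 8.7.6 | no |
| Any-time switch | 8.7.6 | no |

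Cost and effectiveness are promised in one place and only possible in another. Both cannot be followed as written.

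**2. Models available for persistence.** Section 8.7.4 offers a GLM for "normally-distributed data with identity link", which gives a mean difference in days. Section 8.7.2.2, under a secondary objective, names Cox models for discontinuation, switching or either, which give a hazard ratio; no covariates are stated. Section 8.7.6 gives logistic regression for being persistent at one year, which gives an odds ratio and does not use duration. These are three different estimates, and no section says which is primary.

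**3. Timing of the two items.** Cumulative index-drug OOP is C = f + L(m − 1), with first-fill cost f, later-fill cost L and m fills. C rises with m, and m rises with persistence. When L = f, m = C/f. At the same C, a patient whose fills cost twice as much has made half as many, so adjusting for C makes high-cost patients look less persistent even with no true effect. Regimen status can change up to 90 days after index, inside the period in which persistence is measured.

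**4. Coverage when covariates are kept only if p < 0.05.** Assumed: two equal cohorts of n, no true cohort effect, k independent confounders shifted by d SD, outcome coefficient 0.1 each, residual SD 1. The full model is fitted, covariates with p < 0.05 are kept, and the model is refitted (4,000 runs per setting). The expected t for one confounder is about 0.1 × √(2n), so its chance of being kept is about Φ(0.1√(2n) − 1.96):

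- n = 100: t = 1.41, 29%
- n = 200: t = 2.00, 52%
- n = 400: t = 2.83, 81%
- n = 800: t = 4.00, 98%

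If all are dropped, the bias is k × 0.1 × d. For k = 8 and d = 0.3 this is 0.24 residual SD. Simulated coverage of the 95% interval, k = 8, all shifts in the same direction:

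| n per cohort | d = 0.2 | d = 0.3 | d = 0.5 |
|---|---|---|---|
| 100 | 89% | 85% | 69% |
| 200 | 92% | 85% | 75% |
| 400 | 93% | 91% | 87% |
| 800 | 94% | 95% | 93% |

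With mixed directions, or with k = 3, at d = 0.3, coverage is 91–95%. With all confounders kept it is 94–96%.

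**5. Entering month 1–12 index-drug OOP.** Assumed: exponential exit capped at 360 days, a fill every 30 days, lognormal first-fill OOP with CV 0.5, 1 or 2, later fills averaging 20%, 50% or 100% of the first, and log-scale correlation between first and later fills of 0, 0.5 or 1 (300,000 patients per setting). Persistent days are regressed on group and C.

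- OOP comparison (median split, 50% exit in both groups): the unadjusted difference is −0.4 to 1.6 days. Adjusted for C it is −13 to −117 days at correlation 0.5 to 1, and −2 to −46 days at correlation 0. At CV 2 it is only about −2 to −22 days.
- Cycling comparison (exit 50% against 40%, true difference about 22 days): 58–98% of the true difference is kept.

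A fresh run of both simulations for this write-up gave the same figures within simulation error.

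**The case against.** **The plan does supply persistence models.** A reader might infer that persistence duration has no adjusted analysis. The text does not support that: Section 8.7.1.1 promises one, and usable models stand in Sections 8.7.2.2, 8.7.4 and 8.7.6. What stands is that none is designated as primary, with its covariates.

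**The outcome list is open-ended.** A reader might also take absence from the Section 8.7.4 list as exclusion. The list is worded as non-exhaustive, and the section refers back to methods described earlier, so the post-review rule could be meant for additional outcomes only. That is a fair reading, but the sentence does not say so, and the list it introduces contains cost and effectiveness, which other sections promise outright.

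**Year-to-date OOP.** It runs through index, and a reader might infer that it contains the index prescription and so the exposure itself. Its title says pre-index, Section 8.3.1 assigns index-date claims to the post-index period, and neighbouring rows capture other index-date costs and index-drug cost separately. Loose wording is the likelier explanation.

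**The numbers are conditional.** Section 8.7.4 pairs significance with clinical rationale and requires multicollinearity checks; the coverage runs use p-values alone. Cumulative OOP is permitted as a covariate, not planned. Section 8.7.5 mentions regimen status only as an example for predicted costs, and no size was computed for it. No figure measures the effect of choosing outcomes after review. All this stands and limits the magnitude, not the textual defects.

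**Unseen documents.** Section 8.8 mentions a separate analysis plan if applicable, and Section 13 a draft-table workbook. The point applies to the document in hand.

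**Conclusion.** The point holds in this form. Section 8.7.4 makes the final choice of adjusted outcomes depend on results that include cohort tests of post-index measures, against commitments in three other sections. It names no primary adjusted model for persistence duration. It lets significance help choose covariates, keeps no confounder regardless of p-value, and draws on a pool that includes two post-index items labelled as baseline. These are stated rules that can bias estimates if followed, so the sponsor should change them.

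The size is illustrative. In cohorts of 800, or with few confounders, p-value selection costs little. In cohorts of 100 to 200 with many same-direction confounders it costs more: coverage is about 85% at 0.3 SD, and the 69–75% figures need 0.5 SD. The false OOP difference of a few days to over 100 days arises only if cumulative index-drug OOP is entered, and it depends on the assumed OOP distribution. None of these figures is a forecast for this study, and the documents do not show that any analysis has been chosen on results.

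**What to change.** 1. Remove the post-review selection rule for the outcomes in Sections 8.7.1.1, 8.7.2.4 and 8.7.6. Run those adjusted analyses whatever the descriptive results show, and label any outcome added later as exploratory.
2. Before outcome results are seen, name one model already in the plan as the primary adjusted analysis of persistence duration for each primary comparison. An identity-link model on days (workable because one year of post-index enrolment is required) and a Cox model are both defensible; the choice is the sponsor's.
3. Replace significance-based selection with a pre-index confounder set, fixed separately for the OOP and cycling comparisons and kept whatever the p-value. Candidates already defined in Section 8.3 include age, sex, CIRAS, comorbidity score and pre-index conventional DMARD use.
4. Bar covariates measured after index, naming month 1–12 index-drug OOP and 90-day regimen status, and report both descriptively. As a minor clarification, state that year-to-date OOP excludes the index prescription.

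Cost: protocol wording, a few more model runs, and slightly wider intervals from keeping non-significant covariates. In the simulation the widening is about 2–7% at 100 to 200 per cohort with 0.2–0.3 SD imbalance, up to 16% at 0.5 SD, and under 1% at 800.
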